7.2 Safety/Tolerability

Analyses will be performed for all patients having received at least one dose of study drug. The study will use the CTCAE version 4.03 for reporting of non-hematologic adverse events.

8.0 ADVERSE EVENTS

8.1 Experimental Therapy with Carboplatin

For the most recent safety update, please refer to the current Investigator's Brochure or Study Agent Prescribing Information.

8.1.1 Contraindications

8.1.1.1 Carboplatin is contraindicated in patients with a history of severe allergic reactions to cisplatin or other platinum containing compounds

8.1.1.2 Carboplatin should not be employed in patients with severe bone marrow depression or significant bleeding

8.1.2 Special Warnings and Precautions for Use

8.1.2.1 Needles or intravenous administration sets containing aluminum parts that may come in contact with carboplatin should not be used for the preparation or administration of the drug as aluminum can react with carboplatin causing precipitate formation and loss of potency

- 8.1.2.2 Bone marrow suppression is dose dependent and is the dose limiting toxicity. Peripheral blood counts should be monitored frequently during treatment and until recovery is achieved
- 8.1.2.3 Carboplatin can induce emesis which can be more severe in patients previously receiving emetogenic therapy. The incidence and intensity of emesis have been reduced by using premedication with antiemetics
- 8.1.2.4 Although peripheral neurotoxicity is infrequent, its incidence is increased in patients older than 65 years and in patients previously treated with cisplatin
- 8.1.2.5 Allergic reactions to carboplatin have been reported. These may occur within minutes of administration and should be managed with appropriate supportive therapy. There is increased risk of allergic reactions including anaphylaxis in patients previously exposed to platinum therapy
- 8.1.2.6 Carboplatin injection may cause fetal harm when administered to a pregnant woman. If this drug is used during pregnancy, or if the patient becomes pregnant while receiving the drug, the patient should be apprised of the potential hazard to the fetus. Women of childbearing potential should be advised to avoid becoming pregnant

8.1.3 Interaction with other medications

- 8.1.3.1 The renal effects of nephrotoxic compounds may be potentiated by carboplatin

8.1.4 Adverse Reactions

- 8.1.4.1 The most common adverse reactions (incidence $\geq 10\%$) are bone marrow suppression (anemia, thrombocytopenia, and/or neutropenia), nausea, vomiting, mild elevations in alkaline phosphatase, and mild decreases in serum electrolyte values
- 8.1.4.2 Hypersensitivity to carboplatin has been reported in 2% of patients. These allergic reactions have been similar in nature and severity to those reported with other platinum containing compounds and have been successfully managed with standard epinephrine, corticosteroid, and antihistamine therapy

8.2 Experimental Therapy with Palbociclib

For the most recent safety update, please refer to the current Investigator's Brochure or Study Agent Prescribing Information.

8.2.1 Contraindications

- 8.2.1.1 There are no known contraindications

8.2.2 Special Warnings and Precautions for Use

- 8.2.2.1 Neutropenia- Monitor CBC prior to start of palbociclib therapy and at the beginning of each cycle, and as clinically indicated
- 8.2.2.2 Pulmonary embolism- Monitor patients for signs and symptoms of pulmonary embolism and treat as medically appropriate
- 8.2.2.3 Embryo-Fetal toxicity- Can Cause fetal harm. Advise patients of potential risk to a fetus and to use effective contraception

8.2.3 Adverse Reactions

- 8.2.4.1 The most common adverse reactions (incidence $\geq 10\%$) are neutropenia, leukopenia, infections, fatigue, nausea, anemia, stomatitis, headache, diarrhea, thrombocytopenia, constipation, alopecia, vomiting, rash, and decreased appetite

8.2 Adverse Event Reporting Requirements

Adverse event (AE) monitoring and reporting is a routine part of every clinical trial and is done to ensure the safety of subjects enrolled in the studies as well as those who will enroll in future studies using similar agents. Data on adverse events will be collected from the time of the initial study treatment administration through 30 days after the last dose of study treatment. Any serious adverse event that occurs more than 30 days after the last study treatment and is considered related to the study treatment must also be reported. Serious Adverse Events (SAEs) will continue to be followed until:

- Resolution or the symptoms or signs that constitute the serious adverse event return to baseline;
- There is satisfactory explanation other than the study treatment for the changes observed; or
- Death.

The investigator is responsible for the detection, documentation, grading and assignment of attribution of events meeting the criteria and definition of an AE or SAE. The definitions of AEs and SAEs are given below. It is the responsibility of the principal investigator to ensure that all staff involved in the trial is familiar with the content of this section.

Any medical condition or laboratory abnormality with an onset date before initial study treatment administration is considered to be pre-existing in nature. Any known pre-existing conditions that are ongoing at time of study entry should be considered medical history.

All events meeting the criteria and definition of an AE or SAE, as defined in Section 8.3, occurring from the initial study treatment administration through 30 days following the last dose of the study treatment must be recorded as an adverse event in the patient's source documents and on the CRF regardless of frequency, severity (grade) or assessed relationship to the study treatment. All serious adverse events (SAEs) and unanticipated problems (UPs), regardless of causality to study drug, will be reported to the Principal Investigator and also to the Coordinating Center. In addition, SAEs should be submitted to the Coordinating Center and PI any time after the administration of the last dose of palbociclib if the Investigator suspects a causal relationship between the palbociclib and the SAE.

In addition to new events, any increase in the frequency or severity (i.e., toxicity grade) of a pre-existing condition that occurs after the patient begins study treatment is also considered an adverse event.

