10.1.2 Tumor Samples

10.1.2.1 We plan on obtaining tumor samples at screening, at Cycle 2 Day 1, and at progression.

- Screening biopsy sample is mandatory. This must be obtained within the 56 days prior to study treatment. No systemic therapy (i.e. immunotherapy) may have been administered since obtaining the biopsy, if so, a new biopsy is needed.
- Interim Biopsy at Cycle 2, Day 1 (+/- 7 days) is optional and will be offered if safe and clinically feasible
- Biopsy at the time of progression is mandatory however if the treating physician deems biopsy to be either unsafe or not clinically feasible, this must be documented and patient may forego repeat biopsy
- FFPE core biopsy is preferred, However, if not clinically feasible or safe to obtain a core biopsy, contact coordinating site PIs ([name]) as a block made from several FNA passes is acceptable.

[figure not shown]

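### Adverse event collection starts at the first dose, so a serious but recognised complication of a screening biopsy done for the study has no SAE reporting route

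*Combined protocol and SAP*

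**What the plan says.** Section 8.2 (Adverse Event Reporting Requirements) sets the start of collection: "Data on adverse events will be collected from the time of the initial study treatment administration". The rule for source documents and the CRF uses the same window, covering events "occurring from the initial study treatment administration through 30 days following the last dose of the study treatment must be recorded as an adverse event". Anything earlier is dealt with by one sentence: "Any medical condition or laboratory abnormality with an onset date before initial study treatment administration is considered to be pre-existing in nature". The next sentence gives such conditions a place only if they persist: "Any known pre-existing conditions that are ongoing at time of study entry should be considered medical history".

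Section 8.3.1 limits the term adverse event to an occurrence in a patient receiving study treatment.

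On the biopsy, Section 10.1.2 states: "Screening biopsy sample is mandatory. This must be obtained within the 56 days prior to study treatment". If systemic therapy has been given since that sample, "if so, a new biopsy is needed". The calendar in Section 6.1.1 lists the procedure at screening as a biopsy for correlative analysis, and its footnote 14 repeats the 56-day limit and the repeat rule.

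**The concern.** The protocol requires an invasive sample for correlative work and places it before the point at which safety recording begins. Where that biopsy is done because the study needs it, a serious complication is a harm of taking part in the research. Under the current text it need not be recorded as an SAE, sent to the Coordinating Center within 24 hours, or brought into the quarterly safety review described in Section 12.0. What is at stake is oversight of a research procedure. The primary endpoint, the two-stage decision rule and the toxicity stopping rule in Section 11.1 do not depend on it.

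**Working it through.** The plan gives no figure to reproduce. The check is mainly a reading of the sections together, followed by a short sensitivity calculation.

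**Does the biopsy always precede the window?** Yes. Sections 6.1.1 (footnote 14) and 10.1.2 place it in the 56 days before treatment. The Section 8.2 window opens at the first dose, so it covers none of those days.

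**Can a pre-dose complication be an SAE?** No. An SAE (Section 8.3.2) is an adverse event with a serious outcome, and Section 8.3.1 confines adverse events to patients receiving study treatment. Section 8.2 does require SAEs to be reported whatever their causality, but that applies only to events that are already SAEs.

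**Is there an exception for research procedures?** None appears. Section 8.3.1 says that procedures are not themselves adverse events. It does not address complications of a procedure done before dosing.

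**Is the event recorded elsewhere?** Only in part. Section 8.2 sends pre-existing conditions to medical history if they are ongoing at study entry. A complication that has resolved by then has no required safety record under these sections.

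**What about patients who are never dosed?** Under Section 4.0, a patient found ineligible after consent is a screen failure, with no study number and no treatment. The adverse event window never opens for that patient.

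**Which routes remain?**

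| Route | What it catches | What it misses |
|---|---|---|
| Worsening of a pre-existing condition after treatment starts (Sections 8.2 and 8.5) | A complication that becomes more severe or more frequent after dosing | One that resolves or stays stable; any patient never dosed |
| Unanticipated problem (Sections 8.5 and 8.7) | An event that is unexpected, related to research participation and suggestive of greater risk than was known, all three together | A serious complication of a recognised type, which would generally fail the first and third criteria |

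**How likely is an affected event?** The inputs are n, the number of study-driven screening biopsies, and p, the serious complication rate per procedure. The documents give neither. I assume p = 1% to 3% and let n vary up to the planned 40 patients.

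P(at least one) = 1 - (1 - p)^n

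| n | p = 1% | p = 3% |
|---|---|---|
| 10 | 1 - 0.99^10 = 0.10 | 1 - 0.97^10 = 0.26 |
| 20 | 1 - 0.99^20 = 0.18 | 1 - 0.97^20 = 0.46 |
| 40 | 1 - 0.99^40 = 0.33 | 1 - 0.97^40 = 0.70 |

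The row for 40 is the case in which every treated patient's biopsy is done for the study. Biopsied screen failures would add to n.

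**The case against.** The strongest reply is that the safety net is wider than Section 8.2 alone suggests. Unanticipated problems must reach the Coordinating Center within 24 hours, nothing ties them to the first dose, and Section 8.7 turns on relation to research participation, which can include a research biopsy. Worsening after dosing is also an adverse event. This stands, so a reader who infers that a biopsy complication could never be reported goes too far. What remains is the serious event of a known type, which would not normally qualify as unanticipated.

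A second reply is that the biopsy need not be a research procedure. Neither footnote 14 nor Section 10.1.2 says that it must be new or done after consent. A routine diagnostic sample within 56 days, with no systemic therapy since, appears acceptable, and its complications are not research harms. This also stands. It is why the documents do not support treating all 40 patients as exposed, or quoting 33-70% as the expected size. The gap is still real, because the repeat rule foresees biopsies done for the study and Section 1.4 permits prior immunotherapy.

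A third reply is that starting at the first dose suits the objective. Section 2.2.1 concerns adverse events associated with carboplatin and palbociclib. A reader might infer that this objective understates risk, but a bleed before dosing is not an event of drug use, so it does not.

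Finally, complications of the interim biopsy, or of a progression biopsy inside the 30-day window, are already recorded and, if serious, reported regardless of assessed relationship. The lack of a procedure category in Section 8.4.2 affects only how they are labelled.

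The consent pages, CRFs and local IRB standards are not available here, so local arrangements for procedural harms cannot be judged.

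**Conclusion.** The point holds in a limited form. Following the plan as written, a serious, recognised complication of a biopsy done for the study before the first dose has no SAE route, and a biopsied patient who is never dosed has no adverse event window. The unanticipated-problem route and worsening after dosing narrow the gap without closing it.

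Its size depends on how many screening biopsies are study-driven, which the documents do not state. The illustrative chance of at least one such event runs from 10% (10 biopsies at 1%) to 70% (40 biopsies at 3%). Both the rate and the count are assumptions. Sample size, error rates, the primary endpoint and the drug adverse event analysis are unaffected. This is a worthwhile and inexpensive safety improvement, not a flaw in the trial's inference.

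**What to change.** Make three linked changes in Section 8:

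1. In Section 8.2 (Adverse Event Reporting Requirements), require any SAE related to a protocol-required procedure to be reported to the Coordinating Center within 24 hours of awareness, from consent onward and whether or not the patient is later dosed. Collection of drug adverse events still starts at the first dose.
2. Exempt these events from the sentence that classes earlier onset as pre-existing.
3. Align the definition in Section 8.3.1 so that a procedure-related event before dosing can count as an adverse event, and hence as an SAE, for this purpose.

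A procedure option among the attribution choices in Section 8.4.2 would make biopsy events easier to count, but it is optional.

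The cost is a few sentences of text and a few extra SAE forms, including some for consented patients who are never dosed. Because screen failures receive no study number, the form needs some other identifier for them, such as their entry on the Screening and Enrollment Log.

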8.3 Definitions

8.3.1 Adverse Event

An adverse event (AE) is any untoward medical occurrence in a patient receiving study treatment and which does not necessarily have a causal relationship with this treatment. An AE can be any unfavorable and unintended sign (including an abnormal laboratory finding), symptom, or disease temporally associated with the use of an experimental intervention, whether or not related to the intervention.

- *Diagnostic and therapeutic non-invasive and invasive (i.e., surgical) procedures will not be reported as adverse events. However, the medical condition for which the procedure was performed must be reported if it meets the definition of an adverse event unless it is a pre-existing (prior to protocol treatment) condition.*
- *Abnormal laboratory values or test results constitute adverse events if they induce clinical signs or symptoms or require therapy. They are to be captured under the signs, symptoms or diagnoses associated with them.*

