5.2.1 Dosing Interruptions

Patients experiencing any of the following adverse events should have their treatment interrupted/delayed

- Uncomplicated Grade 3 neutropenia (ANC<1000/mm³)
- Grade 3 neutropenia (ANC <1000/mm³) associated with a documented infection of fever ≥ 38.5° C
- Grade 4 neutropenia (ANC <500/mm³)
- Grade 4 thrombocytopenia (platelet count < 25,000/mm³)
- Grade ≥ 3 non-hematologic toxicity (including nausea, vomiting, diarrhea, fatigue, and hypertension only if persisting despite optimal medical treatment)

Appropriate follow up assessments should be done until adequate recovery occurs as assessed by the investigator. Criteria required before treatment can resume are described in Section 5.2.2.

Doses of palbociclib \pm carboplatin infusions may be held as needed until toxicity resolution. Depending on when the adverse event resolved, a treatment interruption may lead to the patient missing all subsequent planned doses within that same cycle or even delay the initiation of the subsequent cycle. If the adverse event that led to the treatment interruption recovers within the same cycle, then re-dosing in that cycle is allowed. Doses omitted for toxicity are not replaced within the same cycle. The need for a dose reduction at the time of treatment resumption should be based on the criteria in Section 5.2.3.

In the event of a treatment interruption for reasons other than treatment-related toxicity (ie non-cancer related surgery) lasting >2 weeks, treatment resumption will be decided in consultation with the co-principal investigators.

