11.0 STATISTICAL CONSIDERATIONS

11.1 Study Design/Study Endpoints

This is an open-label multi-institution single arm Phase II study with a two-stage design. We will power this study to detect a 20% improvement in disease control rate (DCR) with the addition of palbociclib. Based on historical data, the DCR in R/M HNSCC with single agent platinum therapy is 40%^{4,64}. We hypothesize that addition of Palbociclib to carboplatin will increase the DCR at 12 weeks to 60%. We anticipate no loss to followup for this endpoint. The primary clinical objective of this trial is to estimate disease control rate (DCR) at 12 weeks in patients with metastatic head and neck squamous cell cancer treated with carboplatin and palbociclib. Response will be assessed after every two cycles. DCR will be defined as either CR, PR or SD at 12 weeks. The regimen will be considered promising if the true disease control rate is 60% or better. Conversely, if the DCR is 40% or lower, there would be little interest in pursuing this therapy in further studies. In this case, we would like to terminate the trial early and consider a new therapy. The optimal two-stage accrual design has been adopted⁶⁵.

In the first stage, we will accrue 18 response-evaluable patients as defined in section 7.1.1. If 8 or less subjects are considered DCR at 12 weeks, the trial will be stopped and we will conclude that the therapy is ineffective. If we observe 9 or more with disease control (CR, PR, or SD) at 12 weeks, trial will continue to the second stage and an additional 22 response-evaluable patients will be entered. Based on all 40 subjects, if 21 or more patients have achieved disease control, the therapy will be considered promising. If fewer than 21 evaluable subjects achieve DCR at 12 weeks, we will consider the therapy to be ineffective.

Early termination or modification for toxicity

At the initial stage, after 10 patients have been evaluated, if more than 70% experienced grade 3 or 4 toxicity events, the trial will be halted for further safety review and the investigators will consider terminating the study or adjusting the doses. Throughout the study if more than 70% of patient's experience grade 4 toxicity, then the study will be halted for consideration of further adjustments to dosing.

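### The plan conflicts with itself on recording untreated, asymptomatic grade 3-4 cytopenias, and its halting rules omit grade 5; both are minor wording defects

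*Combined protocol and SAP*

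**What the plan says.** **Recording.** Section 8.2 (Adverse Event Reporting Requirements) sends to the source documents and CRF "All events meeting the criteria and definition of an AE or SAE, as defined in Section 8.3". Section 8.3.1 then gives two statements about laboratory values. Its opening paragraph is broad: "An AE can be any unfavorable and unintended sign (including an abnormal laboratory finding". A bullet beneath it is narrower: "Abnormal laboratory values or test results constitute adverse events if they induce clinical signs or symptoms or require therapy", and adds that such values are entered under the associated sign, symptom or diagnosis. Section 7.2 is narrower again: "The study will use the CTCAE version 4.03 for reporting of non-hematologic adverse events".

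Other sections lean the opposite way. Section 5.2.1 opens its list with "Patients experiencing any of the following adverse events should have their treatment interrupted/delayed", and the first item is "Uncomplicated Grade 3 neutropenia". Section 2.3.2.1 has adverse events evaluated partly through routine laboratory work. Sections 8.4.1 and 11.3 apply CTCAE 4.03 to adverse event reporting and tabulation without excluding hematologic events. Section 5.2.2 leaves G-CSF for neutropenia to the investigator.

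**Halting.** Section 11.1 has two rules. After 10 patients: "if more than 70% experienced grade 3 or 4 toxicity events, the trial will be halted for further safety review". Throughout the study, the trigger is more than 70% of patients who "experience grade 4 toxicity, then the study will be halted for consideration of further adjustments to dosing".

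**The concern.** Marrow suppression is the main known toxicity of both drugs, and much of it is found only on a blood count. If a site follows the 8.3.1 bullet, a neutropenia severe enough to interrupt dosing under 5.2.1 need not be recorded as an adverse event, because withholding a dose is not, on a natural reading, therapy. Since G-CSF is discretionary, the same neutrophil count could be an adverse event for an investigator who gives it and not for one who waits. With up to three sites, the hematologic rows of the 11.3 tables could then reflect local habit as well as toxicity. Describing adverse events is a stated secondary objective.

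The halting rules name grade 3 or 4 and grade 4. Read literally, a patient whose only severe toxicity was fatal adds nothing to either numerator, so the worst outcome counts for less than a grade 3 event.

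**Working it through.** The plan gives no operating characteristics for the toxicity rules and no expected number of cytopenias, so it has no figure of its own to reproduce on this point.

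**1. How many patients could the recording rule touch?**

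The inputs are the grade 3-4 neutropenia rates in Section 1.2 (Table 2 and the liposarcoma trial). Grade 3 and grade 4 columns are added on the assumption that each patient is counted once, at worst grade. Patients affected = rate × 40.

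| Source | Grade 3 + grade 4 | Of 40 | If half are symptomatic or treated, number left out |
|---|---|---|---|
| Liposarcoma trial | 50% | 20.0 | 10.0 |
| PALOMA-1 | 48 + 6 = 54% | 21.6 | 10.8 |
| PALOMA-3 | 55 + 10 = 65% | 26.0 | 13.0 |
| PALOMA-2 | 56.1 + 10.4 = 66.5% | 26.6 | 13.3 |

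So 20 to 27 patients would have grade 3-4 neutropenia if these rates carried over. The number the bullet could leave out runs from 0 (all symptomatic or treated), through 10 to 13 (half), to 20 to 27 (none symptomatic or treated). The documents do not give the share. They do show that fever was uncommon: one grade 3 febrile episode in the liposarcoma trial, none in PALOMA-1, and 1.6% reported as serious in PALOMA-2.

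**2. When does omitting grade 5 change the 10-patient decision?**

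More than 70% of 10 means at least 8. Suppose one of the first 10 patients has a fatal event as the only severe toxicity.

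- As written: 7 others with grade 3-4 events give 7/10 = 70%, no halt.
- With *grade 3 or higher*: 7 + 1 = 8/10 = 80%, halt.
- With 6 or fewer others, neither wording halts; with 8 or 9 others, both do.

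So, given one such patient, the wording matters only if exactly 7 of the other 9 have a grade 3-4 event:

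P = C(9,7) × p^7 × (1 − p)^2 = 36 × p^7 × (1 − p)^2

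| Assumed grade 3-4 rate p | P(wording decides) |
|---|---|
| 0.50 | 0.070 |
| 0.60 | 0.161 |
| 0.70 | 0.267 |
| 0.76 | 0.304 |

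The rates are illustrative; 0.76 is the PALOMA-1 any-event figure (59 + 17). The probabilities are conditional on one fatal-only patient having occurred.

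**3. The grade 4 rule.** The same gap exists. At 40 patients, more than 70% means at least 29. Twenty-eight with grade 4 plus one fatal-only patient is 28/40 = 70% (no halt) as written, and 29/40 = 72.5% (halt) if grade 5 counts.

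**4. What the correction does not do.** Three toxic deaths with no other severe event are 0/10 as written and 3/10 once grade 5 counts; neither reaches 8/10. Adding grade 5 makes the count coherent; it does not create a rule for deaths.

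**The case against.** **On recording.** The bullet says *if*, not *only if*, and the paragraph above it admits laboratory findings. Neutropenia is itself a diagnosis and is listed as an adverse reaction of both drugs. Table 4 treats uncomplicated grade 3 neutropenia as a treatment-related toxicity. Section 8.2 classes laboratory abnormalities with onset before treatment as pre-existing, which suggests that later ones are events, and it counts any worsening in grade of a pre-existing condition as an adverse event. The protocol does not define therapy. Blood counts are scheduled, so cytopenias could be tabulated from laboratory data, and monitoring checks completeness.

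These points soften the conflict and show which reading was probably intended. They do not remove it: if every abnormal value were already an adverse event, the bullet's condition would do no work, and the non-hematologic restriction in 7.2 would remain unexplained. It also stands that no omission is demonstrated, only made possible.

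**On halting.** The probabilities in step 2 are conditional. If 1% to 2% of patients were fatal-only (an assumption), the chance that exactly one of 10 is fatal-only and exactly 7 of the other 9 have grade 3-4 events is 10f(1 − f)^9 times the step 2 value. That is about 0.006 to 0.028 at f = 1% and 0.012 to 0.051 at f = 2%. Deaths are reviewed individually in any case: they are SAEs due within 24 hours, fatal events go to the manufacturer immediately, a DSMC oversees safety, and Section 1.3.3 promises frequent toxicity looks. All of this stands and keeps the point small.

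**The opposite objection** is that the recording rule drives the first halting rule, so *minor* is too mild. P(at least 8 of 10) is 0.54 to 0.56 at the 75.5% to 76% any-event rates of PALOMA-2 and PALOMA-1, but only 0.0001 to 0.012 at assumed countable rates of 20% to 40%. That swing requires *toxicity* in 11.1 to mean the narrow 8.3.1 event. Sections 2.3.2.1 and 5.2 and calendar footnote 5 favour CTCAE-graded toxicity, including laboratory toxicity, so 11.1 needs only a clarifying clause on this.

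**Conclusion.** The concern holds, as a minor one. The sections on recording conflict, and following the 8.3.1 bullet with 7.2 literally would drop untreated, asymptomatic grade 3-4 cytopenias from the adverse event tables. The size is uncertain: 0 to 27 of 40 patients, resting on neutropenia rates from other tumors without carboplatin and on an unknown share symptomatic or treated. The halting rules literally omit fatal-only patients. This changes a decision only at the threshold: with probability 0.07 to 0.30 given one such patient in the first 10, and far less unconditionally. The primary endpoint, the two-stage design and the sample size are unaffected.

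**What to change.** - **Sections 7.2 and 8.3.1:** state that hematologic toxicity is graded by CTCAE 4.03 from the scheduled blood counts and recorded as an adverse event whether or not it is symptomatic or treated. If entry burden is a concern, limit this to grade 3 or higher.
- **Section 11.1:** repeat that these laboratory toxicities count, and change the triggers to *grade 3 or higher* and *grade 4 or higher*. The 70% level remains a matter for the investigators and the DSMC.

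The cost is wording in three sections and more adverse event entry. No new procedures are needed, because the blood counts are already scheduled.
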